#### Data acquisition and transmission:

Data will be collected using computer-based self-interview technology (ACASI), and will only be identified with the study's ID of the participant. The use of computer technology for gathering self-report data further enhances overall protection. This software (ACASI) utilizes SSL technology for encrypting of communications between remote computers and the server itself, is HIPAA-compliant, and is currently used in a number of major NIH-funded research studies, including those of the PI.

At the Women and Infants Hospital research site, the link between the participant code number and name will be kept in a password protected file on password protected computer. The accuracy with which data input matches data output using the software will be checked prior to beginning the trial and every five participants thereafter. Data will be checked once per month for out of range values and other quality issues. ACIAS data is password protected and only research personnel will be able to access. Results and the response to whether or not she agrees to participate in the study will be transferred by secure, encrypted electronic file and downloaded to a secure Women and Infants Hospital server. Importantly, no identifying information will be entered into the ACASI. [name] will analyze the data using SPSS software. Booster session data will be recorded using a credit-card size digital audio recorder with data encryption capabilities, which can hold hundreds of hours of

voice recordings so that adherence and competence ratings of the booster sessions can be conducted. These digital recordings which will be labeled with the study identification number and the booster session date and will be transferred to Women and Infants Hospital secure computer server via a secure server access. Access to the audio recordings will be limited to research staff.

Data will be destroyed two years after the completion of the study. We expect the study to be completed by 2024, so we expect the data to be destroyed in 2026.

## **5. PROVISIONS TO MONITOR THE DATA TO ENSURE THE SAFETY OF SUBJECTS**

### **Frequency of Data Safety Monitoring:**

In this study, we will use the FDA definition of serious adverse events (SAEs). The RAs will report SAEs to [name] immediately. Data and safety of patients will be monitored by the PI. At a weekly meeting at Women and Infants Hospital, the PI will review participants' safety and will present participants' clinical status and adverse experiences. Entrance criteria of all participants will be reviewed at these meetings. The PI will ensure that information on participants' adverse effects are systematically collected and evaluated.

[name] will immediately report any adverse events that are observed to the Women and Infants Hospital Internal Review Boards (IRB), DSMB (see below) and NIH. The initial SAE report will be followed by submission of a completed SAE report to both institutions and the DSMB (see below). Outcomes of SAEs will be periodically reported to NIH. A summary of the SAEs that occurred during the previous year will be included in the annual progress report.

An external Data and Safety Monitoring Board (DSMB) will be assembled to evaluate the data and safety to women enrolled in the study. The DSMB will consist of 4 senior doctoral-level/MD board members who have experience in clinical trials and/or IPV intervention research and/or research with perinatal women as the ethical issues involved with a randomized controlled study, as indicated by peer-reviewed journal articles in these areas. We do not anticipate any difficulty in recruiting these qualified, independent, board members as there is a pool of such researchers at several universities in Rhode Island, Michigan, and Massachusetts who have the relevant experience.

The DSMB will convene twice in year 1, once during year 2 to 5 for a meeting. Initially, the Board will convene with the PI to review the study protocol and review the guidelines for data and safety monitoring. This will include establishing standard procedures for daily (whenever there has been contact with a participant) and weekly monitoring by the local internal reviewers (PI and study personnel). At each subsequent meeting, the DSMB will evaluate recruitment, the progress of the trial, subject retention, data quality and confidentiality. In addition, they will review participants' clinical status, rates of adverse events and whether or not there have been any changes in risk to participating subjects. This review will ensure that subject risk does not outweigh study benefits. In the DSMB's review of adverse events, if non-serious adverse events are occurring at a significantly higher rate in one condition than the other, then the DSMB will make appropriate recommendations for changes in the protocol, if needed. If Serious Adverse Events (SAEs) occur at a significantly higher rate in one condition than the other, then the DSMB might consider terminating the trial, if changes to the protocol are unlikely to address the high occurrence of the SAEs. We do not anticipate that this will occur, because we have taken several steps to avoid or protect against the occurrence of SAEs as outlined in the Section on Protection against Risk. A report generated from each of these meetings will be retained at each study site and will be forwarded to the each study site's IRBs and to NICHD in the annual progress report.

The DSMB will be available to convene outside of the appointed meeting schedule, if necessary, due to concerns regarding a particular subject, or due to any troublesome developments in subjects'

experiences during the study. The DSMB will make appropriate recommendations for changes in the study protocol, if needed. The safety of participants will be monitored during each contact with study participants. Both anticipated and unanticipated adverse events and problems will be formally monitored and recorded. Unanticipated serious adverse events or problems will be reported to Women and Infants Hospital and University of Michigan IRBs and to NICHD within 24 hours.

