### **Intervention Conditions**

#### **1. Reach Out for a Safe Environment (ROSE)**

ROSE participants will receive a 40-minute online/computer-based intervention immediately after their baseline assessment and an in-person 30-minute booster session conducted by interventionists within a month after the intervention. The online intervention will be sent by email as a link (URL) to the intervention. The link will not contain any wording that could reveal the nature of the intervention/study. The link will become inactive once the intervention is completed. If online, research staff will call ROSE participants after the intervention in case they have questions after the completion of the online session. If on site, research staff will be available after the intervention in case ROSE participants have questions after the completion of the session. The ROSE Program is specifically tailored, innovative and relevant to diverse, racial and ethnic perinatal women in a number of ways including the images and content used in the intervention. It will also be tailored on the current IPV risk assessment, pregnancy or postpartum status of each participant, will be designed to reach participants across levels of motivation for change, and will follow guidelines for brief interventions as recommended by the ACOG. The content of ROSE is theory-driven, consistent with the MI model of behavior, and consistent with the literature on effective interventions that address IPV.

Possible distress due to sensitive items will be noted clearly in the informed consent information sheet (for screening) and in the written informed consent form (for participants). All participants will be told that they can skip any question or quit at any time if they become uncomfortable. To further address possible distress due to sensitive items, participants will be asked by the research assistant if anything during the assessment or intervention has made them feel upset. At a minimum, all participants indicating some distress will be given a list of referral options. If in treatment women will be encouraged to contact their mental health provider. Suicidality will not be assessed during the course of this research study.

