## **2. Control Condition**

The control condition will be the same, well-validated, attention, time and information-matched online/computerized control intervention condition used successfully in our previous studies with perinatal women, in which ratings of acceptability were equally high among intervention and control group participants. The online intervention will be sent by email as a link (URL) to the intervention. The link will not contain any wording that could reveal the nature of the intervention/study. The link will become inactive once the intervention is completed. This condition consists of a series of questions regarding television show preferences and viewing a brief series of videos of popular entertainers/shows, with subsequent requests for ratings of subjective preference. This content will serve to control time and help to limit inadvertent therapeutic effects that plague control groups in brief intervention research. The telephone booster session will be comparable in time to ROSE's telephone booster session (10-15 minutes). The booster session will consist of an interventionist reviewing with the participant her ratings of the various of popular entertainers/shows that she watched in the intervention, discussing with the participant more in-depth her preferences, and discussing any other forms of entertainment/shows that participant has watched, heard of, or would like to see.

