**Protection against risk**

We will take the following steps to protect against risks associated with this research project:

*We will minimize the risk of breach of confidentiality.*

Risk of social or legal consequences as a result of disclosure of IPV within the past year will be dealt with in several ways. We will minimize the potential risks due to loss of confidentiality by strictly adhering to the guidelines for research outlined by Women and Infants Hospital IRB, Rhode Island state law and the DHHS Federal Policy for the Protection of Human Subjects (45 CFR Part 46 Subpart D). As described in the previous section, there will be full informed phone or in-person consent prior to participation in the study (a two-part consent process). Participant data will be encrypted in transit between user and server. No identifying information will be entered into the ACASI. The use of a linking table will provide the participant with confidentiality as the link between the participant code number and name will be kept in a password protected file on password protected computer. Lastly, potential participants will be informed of the situations in which they may not be protected under the Certificate of Confidentiality. No information about participants will be released without their permission or where required by law.

Possible distress due to sensitive items will be noted clearly in the informed consent information sheet (for screening) and in the written informed consent form (for participants). All participants will be told that they can skip any question or quit at any time if they become uncomfortable. To further address possible distress due to sensitive items, participants will be periodically asked by the research assistant (RA) if anything the RA has asked or done is making them feel upset right now. For both the online intervention and in-person computer-delivered intervention, the research assistant will contact the participant after 40 minutes, the time it takes to watch the intervention and inquire if anything in the intervention distressed her. At a minimum, all participants indicating some distress will be given a list of referral options. If in treatment women will be encouraged to contact their mental health provider.

*We will minimize the risk of study-related partner violence.*

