The online intervention will be sent to a secure email as a link (i.e., URL) to the intervention. The link will not contain any wording that could reveal the nature of the intervention/study. The link will become inactive once the intervention is completed. Women can hit the stop button at any time during the intervention and it will stop immediately. Women can also click an escape button during the intervention that will redirect her to the Google search page. The link (URL) can then be sent again and the participant can continue with the intervention from the place where she stopped. If the woman chooses to view the online intervention remotely through their iPhone or iPad, they will have to download the CIAS app from the app store to open the link for the intervention. The app itself has as its only description as "Medical" and "Wayne State University". The image of the app has a yellow heart with a stethoscope. When the participant uses the emailed link to view the intervention, the CIAS app will automatically open. This is the only time the CIAS app will show information about the study. If another person were to open the app at another time, they would be unable to see the completed intervention. Although the proposed intervention seeks to help a woman to develop strategies for keeping herself safe, it is possible that a woman who participates in the study might be at increased risk of partner violence because of increased assertiveness. At each follow-up assessment, our assessment of community resource use will ask about participants' visits to emergency rooms, health professionals, etc. The Composite Abuse Scale (CAS) will be administered to monitor abusive experiences in the context of a woman's relationship since the last assessment. Women will be asked at follow up sessions about any instances of hospitalizations, emergency room visits, life threatening threats of IPV, rape, or sexual assault to better gather information regarding any potential adverse events to report to the Data Safety Monitoring Board (DSMB) (see section D5 below for more details), which will monitor these events.

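### The DSMB's between-arm adverse-event comparison is not protected from unequal ascertainment before week 6, chiefly because the two boosters differ in content and no common harm questions are set for them

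*Combined protocol and SAP*

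**What the plan says.** **The comparison.** Section 5 (Frequency of Data Safety Monitoring) says that "The safety of participants will be monitored during each contact with study participants" and that "Both anticipated and unanticipated adverse events and problems will be formally monitored and recorded". The DSMB may recommend protocol changes "if non-serious adverse events are occurring at a significantly higher rate in one condition than the other". For serious events, "If Serious Adverse Events (SAEs) occur at a significantly higher rate in one condition than the other, then the DSMB might consider terminating the trial", provided that protocol changes are unlikely to solve the problem. No test, denominator or source of events is defined for either comparison.

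**The contacts before week 6.** The Study Design section gives both arms a phone booster within 4 weeks of baseline. For control, "The booster session will consist of an interventionist reviewing with the participant her ratings of the various of popular entertainers/shows". The Interventionists section describes the ROSE booster as scripted and based on motivational interviewing, with training in empowerment principles.

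On the contact just after the session, the ROSE section says: "If online, research staff will call ROSE participants after the intervention in case they have questions after the completion of the online session". The Control Condition section describes no such call. The section Protection against risk, however, covers both online and in-person delivery and does not name an arm: "the research assistant will contact the participant after 40 minutes, the time it takes to watch the intervention and inquire if anything in the intervention" caused her distress.

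**The matched questions.** The same section says: "Women will be asked at follow up sessions about any instances of hospitalizations, emergency room visits, life threatening threats of IPV, rape, or sexual assault". It also provides, at each follow-up, questions on emergency-room and health-professional visits and the Composite Abuse Scale (CAS) for the period since the last assessment. None of this is limited to one arm.

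**The concern.** If events may be recorded from any contact, the comparison between arms is fair only when the contacts give each arm the same opportunity to report. A motivational conversation that follows up a partner-violence intervention probably prompts mention of a threat, an injury or distress more readily than a conversation about television does. With equal true harm, the recorded rate could then be higher in ROSE.

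Two errors are possible. The DSMB could see an excess that is only better detection, or it could dismiss a true excess as better detection. The second matters here because the protocol itself raises the possibility that ROSE increases partner violence through greater assertiveness (Protection against risk). This comparison is the one meant to show whether that happens.

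**Working it through.** **1. Contacts after randomisation, by arm.**

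| Contact | ROSE | Control | Same questions in both arms? |
|---|---|---|---|
| Post-session contact | Call or on-site availability (ROSE section); distress query (Protection against risk) | No call in the Control Condition section; distress query if Protection against risk covers both arms | Unclear: the sections must be reconciled |
| Booster, within 4 weeks | Motivational interviewing and empowerment | Entertainment preferences | No common adverse-event questions stated |
| 6 weeks, 3, 6 and 12 months | Harm list, service use, CAS | Same | Yes |

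The count is 6 planned contacts against 5 if the call is for ROSE only, and 6 against 6 if the distress query covers both arms. Booster mode and length are also inconsistent: by phone (Study Design), in person for 30 minutes (ROSE section), and by telephone for 10-15 minutes in both arms (Control Condition).

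**2. Which events are exposed.** The follow-up list names hospitalizations, emergency visits, life-threatening threats, rape and sexual assault. Such an event in weeks 0-6 is asked about at week 6 in both arms. Distress and lesser events that arise after the session are not on that list, yet non-serious events are a separate basis for DSMB action.

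**3. Illustration of size.** The plan has no figure to reproduce. From the documents come 93 per arm and the 6-week visit. Everything else is assumed:
- true risk p is 20%, 30% or 40%, equal in both arms, with a constant event rate over time;
- in the first 6 weeks, capture is c in control and r in ROSE; after that it is r in both arms;
- the test is a pooled two-proportion z-test, two-sided 5%, with exact binomial enumeration.

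Share of follow-up in the first 6 weeks:
- over 12 months, w = 6/52 = 0.115;
- at a review 26 weeks into even accrual, w = (6 x 26 - 6²/2) / (26²/2) = 138/338 = 0.41.

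Recorded risk is p x r in ROSE and p x [w x c + (1 - w) x r] in control. For example, with p = 0.30, c = 0.60, r = 0.90 and w = 0.115, ROSE has 0.270 and control has 0.30 x 0.865 = 0.260.

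Chance that ROSE is flagged as significantly higher, for p = 20% / 30% / 40%:

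| Capture, control vs ROSE | 12 months, 93 per arm | 26-week review, 93 per arm | 26-week review, 20 per arm |
|---|---|---|---|
| 0.75 vs 0.90 | 2.9 / 3.1 / 3.3% | 4.0 / 4.8 / 5.6% | 3.1 / 3.5 / 3.8% |
| 0.50 vs 0.75 | 3.2 / 3.5 / 3.8% | 5.9 / 7.4 / 9.2% | 3.6 / 4.2 / 4.9% |
| 0.60 vs 0.90 | 3.3 / 3.7 / 4.1% | 6.4 / 8.5 / 10.8% | 3.9 / 4.6 / 5.4% |

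With equal capture the figure is about 2.5%. The middle column is an upper bound, since all 93 per arm would not be enrolled so early. The 20 per arm is an assumption.

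**The case against.** The strongest reply is that most safeguards are already the same in both arms. Monitoring at each contact is not arm-specific, so the control booster is a monitored contact too. The same interventionists are trained for both boosters, and both trainings include emergency role-plays. Research assistants ask participants about distress without regard to arm. Section 5 gives the DSMB's first meeting the task of setting standard monitoring procedures. The DSMB has discretion, no automatic rule, and can weigh where a report came from. No section says that the ROSE booster asks about harms; its partner-violence content is inferred from its purpose and training.

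Much of this stands, and it rules out three stronger readings that a reader might infer:
- **Only ROSE has a staff contact after the session.** The ROSE section alone suggests this, but Protection against risk describes a contact not limited to ROSE, possibly the same one.
- **The comparison is biased.** The documents show a missing safeguard with a likely direction, not a demonstrated bias.
- **The false-signal risk is large.** Applying the capture gaps above to all events over the year would give 8-14%, 18-35% and 21-44%. The asymmetry, however, lies before week 6, and from then on the scheduled questions are the same.

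What the reply does not remove is the booster. It is led by an interventionist, its content differs by arm, and no common harm questions are set for it. The standard procedures are assigned to a later meeting and are not described.

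**Conclusion.** The point holds as a gap in the plan. Nothing makes adverse-event elicitation the same in both arms before week 6, and the likely direction is towards more recorded events in ROSE. The booster is the main source. The post-session call is a possible second source that depends on how the sections are reconciled.

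The size is modest. For an assumed 20-40% event risk and the capture gaps shown, the chance of a false signal against ROSE rises from 2.5% to about 3-4% at 12 months, and to roughly 3-11% at an early review. The documents give no event or capture rates, so these figures show scale only. The effect is mainly on non-serious events and early reviews. For serious events the 12-month effect should be small, because the 6-week questions recover most of them; women who miss that visit are an exception. The change is worth making because it is cheap and the comparison bears on a harm that the protocol itself foresees.

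**What to change.** 1. Close the booster in both arms with the same short scripted questions on distress and adverse events.
2. Add a source field to the adverse-event form: scripted question or spontaneous report, and at which contact. This is still needed with step 1, because the ROSE conversation may prompt disclosure before the script is reached.
3. State in section 5 that the DSMB sees the arm comparison twice: for all events, and for events elicited identically in both arms. Every event is still reported and acted on individually. Using only identically elicited events is not recommended, since it could hide harm that surfaces only in conversation.
4. Reconcile the post-session contact (ROSE section, Control Condition, Protection against risk) and the booster's mode and length (Study Design, ROSE section, Control Condition).

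The cost is one or two minutes per booster, one form field and a short addition to section 5. No extra staff or visits are needed.

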## 6. WITHDRAWAL OF SUBJECTS

Study staff will be trained on understanding the various potential risks of participation in this study, as explained above, in the section "Risks and Benefits." As explained in this section, various procedures will be put into place to mitigate these potential risks. However, if when discussing the safety of a subject's participation in the study, study staff decides that stopping a subject's participation is necessary for safety reasons, then study staff will withdraw the subject from the study. As explained in the "Risks and Benefits" section, we anticipate that potential circumstances in which this might need to occur include breaching of confidentiality, coercion of participants, participant discomfort, the occurrence of study-related partner violence, and/or social or legal consequences related to study participation.

If participants voluntarily withdraw from the research, study staff will keep the data that has already been collected, and will use this data in the study analysis procedures. If a participant is physically present when she decides to withdraw from the study, she will be checked in with by research staff, be given any relevant informational handouts if it is safe for her to receive and take with her, and be given any relevant referrals.

